4. LIST OF ABBREVIATIONS AND DEFINITIONS OF TERMS

The following abbreviations and specialist terms are used in this study protocol.

Table 2: Abbreviations and Specialist Terms

Abbreviation or Specialist Term	Explanation
3D	Three-dimensional
AE	Adverse event
ALP	Alkaline phosphatase
ALT	Alanine aminotransferase
AST	Aspartate aminotransferase
AUC	Area under the curve
BMI	Body mass index
BUN	Blood urea nitrogen
cc	Cubic centimeters
CFR	Code of Federal Regulations (US)
cm	Centimeter
CT	Computed tomography
CTCAE	Common Terminology Criteria for Adverse Events
ECG	Electrocardiogram
eCRF	Electronic case report form
EDC	Electronic data capture
ET	End of treatment
FDA	Food and Drug Administration (US)
GCP	Good Clinical Practice
GLP	Good Laboratory Practice
Gy	Gray
HbA1c	Hemoglobin A1c
HDPE	High-density polyethylene
HIV	Human immunodeficiency virus
hr	Hour
ICH	International Conference on Harmonization
IFN γ	Interferon-gamma
IMRT	Intensity modulated radiation treatment
IRB	Institutional Review Board
ITT	Intent-to-Treat
IWRS	Interactive Web Response System
LLOQ	Lower limit of quantitation

Abbreviation or Specialist Term	Explanation
MCH	Mean corpuscular hemoglobin
MCHC	Mean corpuscular hemoglobin concentration
MCV	Mean corpuscular volume
µg	Microgram
mL	Milliliter
µM	Micromolar
mm Hg	Millimeters of mercury
n	Number of patients
NCI	National Cancer Institute
NF-κB	Nuclear factor kappa-light-chain-enhancer of activated B-cells
ng	Nanogram
Nrf2	Nuclear factor erythroid-derived 2-related factor 2
NO	Nitric oxide
NOAEL	No observed adverse effect level
NQO1	NAD(P)H:quinone oxidoreductase 1
PD	Pharmacodynamic
PK	Pharmacokinetic
RBC	Red blood cell
RT	Radiation therapy
SAE	Serious adverse event
SAP	Statistical analysis plan
SOP	Standard operating procedure
STAT	Skin toxicity assessment tool
TBL	Total bilirubin
TNM	Cancer classification system based on assessment of the Tumor, lymph Nodes, and Metastases
US	United States
WBC	White blood cell
WK	Week
WOCBP	Women of child bearing potential

5. INTRODUCTION

5.1. Background on RTA 408

Natural triterpenoids, such as oleanolic acid and ursolic acid, are derived from plant extracts and have been used extensively in Asian medicine for their anti-inflammatory and anticancer properties (Liu 1995). A series of semi-synthetic triterpenoids was prepared based on the structure of oleanolic acid and tested to identify compounds optimized for their ability to inhibit the induction of nitric oxide in primary mouse macrophages treated with interferon-gamma (IFN- γ) (Honda 1999). RTA 408 is a novel oleanane triterpenoid and part of this class of compounds. Mechanistic studies have revealed that RTA 408 and the semi-synthetic triterpenoids are potent activators of nuclear factor erythroid derived 2-related factor 2 (Nrf2) and inhibitors of nuclear factor kappa light-chain-enhancer of activated B-cells (NF- κ B), and thus induce an antioxidant and anti-inflammatory phenotype.

The transcription factor Nrf2 regulates the expression of numerous antioxidant and anti-inflammatory genes. Activation of Nrf2 induces the expression of a battery of cytoprotective genes, which results in a coordinated cellular effort to protect against oxidative insult, highlighted by increased anti-oxidative capacity, induction of glutathione synthesis, and conjugation and efflux of potentially harmful molecules. RTA 408 and the semi-synthetic oleanane triterpenoids are among the most potent activators of Nrf2 identified to date (Sporn 2011, Dinkova-Kostova 2005). The structure and activity profile of this class resembles that of the cyclopentenone prostaglandins, the endogenous regulators of Nrf2, which also inhibit NF- κ B and play an important role in the resolution of inflammation (Levonnen 2004, Cernuda Morollon 2001, Cuzzocrea 2003, Kawamoto 2000, Rossi 2000, Straus 2000). RTA 408 exhibits efficacy in a broad range of animal models of diseases involving inflammation and oxidative stress, including models of radiation-induced skin and organ damage, cancer, idiopathic pulmonary fibrosis, chronic obstructive pulmonary disease, rheumatoid arthritis, multiple sclerosis, asthma, and sepsis.

Reata has demonstrated that topical dermal administration of RTA 408 activates the Nrf2 pathway and increases expression of Nrf2 target genes in both the dermis and epidermis of various nonclinical species (Reisman 2013), as well as in human skin explants *ex vivo*. RTA 408 is highly effective in rodent models of radiation-induced dermatitis and also protects against organ damage from whole-body irradiation and radiation-induced oral mucositis.

Dermal application of RTA 408 Lotion was well-tolerated in a variety of nonclinical studies. In dermal Good Laboratory Practice (GLP) toxicity studies with up to 13 weeks of twice-daily dosing, no evidence of skin toxicity related to RTA 408 Lotion was observed in either rats or minipigs with doses as high as 8% RTA 408 Lotion. Further, in marked contrast to the negligible systemic exposure that has been observed in the Phase 1 clinical study with dermal dosing of RTA 408 Lotion to healthy volunteers, meaningful systemic exposure was observed in rats and minipigs. In the 14-day dermal GLP toxicity studies, systemic exposures, based on the area under the curve (AUC_(0-24hr)), of up to 5.3 hr* μ g/mL in rats and 4.9 hr* μ g/mL in minipigs at the maximum feasible dose of 8% RTA 408 Lotion were not associated with any adverse effects and consequently, the no-observed-adverse-effect-level (NOAEL) was 8% for both species. In the 13-week minipig dermal GLP toxicity study, systemic exposures (AUC_(0-24hr)) up to

1.7 hr* μ g/mL were also not associated with any adverse findings, and thus, the NOAEL was also 8% RTA 408 Lotion. In the 13-week rat dermal GLP toxicity study, systemic exposures exceeded those associated with adverse effects in chronic oral toxicity studies in rats (*i.e.*, 4.6 hr* μ g/mL in the 13-week dermal study vs. 2.3 hr* μ g/mL in the 6-month oral dosing study). The liver and kidney were identified as target organs in the 13-week rat dermal GLP toxicity study, consistent with findings from the oral toxicity studies, and the resulting NOAELs were 0.3% RTA 408 Lotion in females and < 0.3% RTA 408 Lotion in males. Furthermore, the systemic toxicity potential of RTA 408 has been extensively studied in rats and monkeys, with daily oral administration for up to six months in rats and nine months in monkeys. Overall, based on an integrated assessment of the nonclinical data, and based on the demonstrated low systemic exposure to RTA 408 in healthy human volunteers after topical administration, it is concluded that RTA 408 Lotion has an acceptable safety profile for topical use as indicated in this Phase 2 study in female patients at risk for radiation dermatitis.

A Phase 1 study (408-C-1305) was completed to evaluate the safety, local pharmacodynamics (PD), and systemic pharmacokinetics (PK) of RTA 408 following topical application of RTA 408 Lotion to healthy volunteers. The Phase 1 study was conducted in three parts. In Part A of the study, RTA 408 Lotion Vehicle and RTA 408 Lotion (0.5%, 1%, and 3%) were each concurrently applied to a small skin surface area (four individual 4-cm² sites; 16 cm² total area) twice daily for 14 days. The maximum tolerated drug concentration in Part A was 3% RTA 408 Lotion. In Part B, RTA 408 Lotion (3%) was applied topically twice daily for 14 days to a larger skin surface area (~100 cm²). In Part C, 3% RTA 408 Lotion was applied topically twice daily for 28 days to an even larger skin surface area (~500 cm²). Approximately 32 healthy adult volunteers were enrolled in the Phase 1 study with 12 volunteers in Part A, 10 volunteers in Part B, and 10 volunteers in Part C.

5.2. Background on Radiation-Induced Dermatitis

Radiation dermatitis is experienced by almost all patients (up to 95%) receiving radiation therapy for cancer (Ryan 2012). Radiation dermatitis can be a serious condition because, in addition to its direct physical complications and the resulting impact on overall quality of life, it can also be a dose-limiting toxicity requiring changes to the prescribed course of radiation therapy. The most common strategy employed in an attempt to prevent or minimize radiation dermatitis involves moisturization of the irradiated area, use of a mild soap to keep the area clean, and minimizing exposure to potential mechanical irritants, such as scratching and rough clothing. However, this strategy has been shown to lack clinically significant efficacy (Salvo 2010). Consequently, there is a clinical need for new treatments that are effective in protecting against radiotherapy-induced oxidative stress and the subsequent development of radiation dermatitis.

RTA 408 Lotion has shown significant efficacy in mouse models of radiation dermatitis with both fractionated and acute radiation regimens. In these models, disease severity was evaluated using a 5-point clinical scoring scale, similar to the CTCAE scale used in clinical practice. In the fractionated radiation dermatitis model, RTA 408 Lotion was effective in decreasing the severity of dermatitis in mice that received a cumulative radiation dose of 60 Gray (Reisman 2014). Specifically, RTA 408 Lotion treatment was associated with a lower incidence of animals that developed severe dermatitis and improved histology scores compared with vehicle controls. Further, RTA 408 Lotion is unlikely to interfere with radiation therapy, as RTA 408 has demonstrated enhanced therapeutic efficacy when orally administered concomitantly with radiation therapy in a mouse xenograft cancer model, and an oral dosage form of RTA 408 is currently being studied in a Phase 1 study in patients with advanced cancers. Based on these data, Reata believes that RTA 408 Lotion may effectively prevent and mitigate radiation dermatitis in oncology patients undergoing radiation therapy.

5.3. Rationale

This randomized, double-blind, vehicle-controlled, parallel-group trial will study the efficacy, tolerability and safety of two concentrations of RTA 408 Lotion (3% and 0.5%) versus vehicle in patients with breast cancer for whom radiation therapy is recommended. The primary outcome will be the change in dermatitis grade measured with Common Terminology Criteria for Adverse Events (CTCAE, Version 4.03) following administration of RTA 408 Lotion compared to administration of vehicle.

6. TRIAL OBJECTIVES AND PURPOSE

6.1. Primary Study Objectives

The primary objectives of this study are the following:

1. To determine the time-averaged effect on radiation dermatitis grade measured with Common Terminology Criteria for Adverse Events (CTCAE, Version 4.03) following 3D conformal radiation therapy to the breast and concomitant administration of RTA 408 Lotion (0.5% and 3%) compared to administration of vehicle.
2. To evaluate the safety of RTA 408 Lotion

6.2. Secondary Study Objectives

The secondary objectives of this study are the following:

1. To determine the mean maximum radiation dermatitis grade measured with CTCAE of RTA 408 Lotion (0.5% and 3%) compared to administration of vehicle
2. To determine the proportion of patients with treatment success, defined as post-baseline maximum dermatitis grade < 2 using the CTCAE criteria following administration of RTA 408 Lotion compared to administration of vehicle
3. To determine the mean duration of grade ≥ 2 radiation dermatitis using the CTCAE criteria following administration of RTA 408 Lotion compared to administration of vehicle
4. To determine the extent of systemic exposure to RTA 408 following administration of RTA 408 Lotion following radiation therapy
5. To evaluate patient-reported outcomes (Skindex-16)

7. INVESTIGATIONAL PLAN

7.1. Overall Study Design

This randomized, double-blind, vehicle-controlled, parallel-group study will assess the safety, tolerability and efficacy of RTA 408 Lotion (0.5% or 3%) versus vehicle in the treatment of patients at risk for radiation dermatitis. Eligible patients will be randomized using a 1:1:1 assignment ratio to receive RTA 408 Lotion 0.5%, RTA 408 Lotion 3%, or vehicle 1 week (\pm 2 days) prior to initiation of radiation therapy. Randomization will be stratified by smoking status (smoker or ex-smoker versus non-smoker) and breast cancer treatment prior to radiation therapy (mastectomy versus lumpectomy/partial mastectomy).

Study drug application will start approximately 1 week prior to scheduled initiation of radiation therapy with twice daily applications continuing throughout the duration of radiation therapy (*i.e.*, 5-6 weeks) and two weeks following completion of radiation therapy, for an expected total of up to 9 weeks of study drug application. In cases where radiation treatment is delayed (*e.g.*, delayed start of radiation treatment or radiation treatment interruptions), the total study drug application period may be extended from the expected 8-9 weeks up to a maximum of 13 weeks. Study lotion is to be applied twice daily.

On days of morning radiation treatments, the patient will apply the study drug at the radiation treatment center immediately after the radiation therapy concludes and at night before bed. On days of afternoon radiation treatments, the patient will apply the study drug in the morning at least 4 hours before radiation treatment and at night before bed. For each application of study drug treatment, a thin layer of lotion will be applied to the irradiated area. RTA 408 Lotion or vehicle lotion should never be applied immediately before radiation treatment, and any residual lotion from a prior application should be removed prior to radiation treatment.

Following randomization, patients will be assessed in person at weekly visits during administration of study treatment. A follow-up visit will occur 4 weeks after last application of RTA 408 Lotion or vehicle. Due to the variation in radiation treatment schedules, exact study days or procedures may be shifted to fall within a window of 2 days based on radiation treatment schedules. However, all enrolled patients must continue to apply RTA 408 Lotion for two weeks after the completion of radiation.

7.2. Number of Patients

Approximately 177 patients (59 per treatment group) are to be enrolled in this study.

7.3. Treatment Assignment

Patients who qualify for the study will be randomized with a 1:1:1 assignment ratio to receive RTA 408 Lotion 0.5%, RTA 408 Lotion 3%, or vehicle. Randomization will be stratified by smoking status (smoker or ex-smoker versus non-smoker) and breast cancer treatment prior to radiation therapy (full mastectomy versus partial mastectomy or lumpectomy). Treatment assignments will be managed by an IWRS system.

7.4. Criteria for Study Termination

Although the Sponsor intends to complete the study, the Sponsor reserves the right to discontinue the study at any time for clinical or administrative reasons, or if required by regulatory agencies. If the Sponsor discontinues the study, all study treatment will be discontinued, and the investigator will be responsible for any additional therapy to be administered.

7.5. Schedules of Assessments

[Table 3](#) lists the overall schedule of assessments for the study.

Table 3: Overall Schedule of Assessments

Assessment	Screening Period	Randomization and Run In Period	Day 1 of Radiation Treatment	Concurrent with RT					Last day of RT	After RT	Last day of Study Drug	ET / Follow-up
				4 ^d	5 ^d	6 ^d	7 ^d	8 ^e				
Study Visit	1 ^a	2 ^b	3 ^c	RT WK 2	RT WK 3	RT WK 4	RT WK 5	RT WK 6	Last Day of RT ^d	Post-RT WK 1	Post-RT WK 2 / End of Study Drug Administration	Post-RT WK 6 / ET / Follow-up Visit
Visits or Visit Procedures may fall within a window of ± 2 days for a total of 2 days ⁱ	Up to 45 days	Randomization Visit - First Day of Study Lotion Application for Run-In Period 7 days prior to RT ^b	RT WK 1 ^c									
Informed consent	X											
Inclusion/ Exclusion	X	X										
Demographics and baseline disease characteristics	X											
Fitzpatrick skin type	X											
Prior and Concomitant medications	X	X	X				X		X		X	X
Medical history ^j	X											
Height	X ^k											
Weight and BMI	X ^k					X			X			X
Vital signs	X ^k					X			X		X	X
Physical exam	X ^k											X
Smoking status	X											
Chest wall separation	X											
Measurement of radiation treatment skin surface area ^l (Prior to RT)	\leftarrow X ^l \rightarrow											
Breast volume (lumpectomy and breast-conserving surgery patients) ^m	X											
Randomization		X										
Pregnancy test WOCBP ⁿ	X ^t	X			X					X		X
Dispense/ Weigh study drug ^o		X			X			X				
Study drug application/diary ^p	\leftarrow X \rightarrow											
Collect / Weigh study drug					X			X			X	
Radiation treatment ^q			X	X	X	X	X	X				
Dermatitis assessment ^r			X	X	X	X	X	X	X		X	X
Skindex-16 assessment ^s			X						X		X	X
Adverse event collection		X	X	X	X	X	X	X	X	X	X	X
Clinical chemistry	X ^t				X			X			X	X
Hematology	X ^t					X			X		X	X
Urinalysis and microscopy	X ^t					X			X		X	X
PK sample ^u			X		X				X		X	X
Photograph collection				X ^v					X ^v		X	X
End of Study												X

^a The Screening Period (Visit 1) may last up to 45 days prior to Randomization (up to 52 days prior to Day 1 of RT).

^b Visit 2 (7 days prior to radiation treatment) is the day of randomization and application of the first dose, and must occur at least 5 and no more than 9 days prior to the first day of radiation treatment. If the start of radiation treatment is delayed, patients should continue administering study drug twice daily until the first dose of radiation up to a maximum of 14 days. If the time from randomization to first dose of radiation exceeds 14 days, the medical monitor should be contacted to decide on an appropriate action. Patients may be randomized after meeting the inclusion / exclusion criteria and before study drug lotion is first administered as long as patients apply study drug lotion for at least 5 days prior to the first day of radiation treatment. Patients with either morning or afternoon randomizations may apply lotion in the clinic and again before bedtime for two doses on that day.

^c Visit 3 should occur on the day of the first radiation treatment. If radiation treatment is in the morning, the radiation treatment will be the third to last procedure (radiation treatment > study drug application > PK). If radiation treatment is in the afternoon, radiation treatment will be the second to last procedure, and the last procedure will be PK, as study drug will have been applied at least 4 hours prior to radiation treatment.

^d Study visits during radiation treatment therapy must occur weekly beginning with Day 1 of radiation treatment.

^e At the end of radiation treatment, patients must complete Visit 9 assessments. Visit 9 must be the last day of the 10 – 16 Gy boost. Visit 8 is needed for patients who require radiation therapy for 6 weeks. If radiation therapy is extended longer than 6 weeks, then assessments at Visit 8 should be repeated weekly until the end of radiation visit (Visit 9). A weekly study visit should not be performed if the visit falls 1 or 2 days prior to the last day of radiation (Visit 9), or 1-2 days after the last day of radiation.

^f Visit 10 should occur approximately 1 week (7 calendar days) after the completion of radiation therapy (Visit 9).

^g Visit 11 should occur approximately 1 week (7 calendar days) after Visit 10 (*i.e.*, 2 weeks after the completion of radiation therapy).

^h Follow-up visit will occur approximately 4 weeks after the final study drug application. These procedures should be performed at the end of study and for early termination.

ⁱ The ± 2 day window is a two-day allowance within which the visit or visit procedures may occur around the scheduled visit date.

^j Medical history includes collection of surgery type (lumpectomy, partial mastectomy (breast conserving surgeries), or full mastectomy). If the patient is to undergo post-mastectomy reconstruction before radiation treatment, the type of reconstruction should be recorded as well.

^k Procedures that are to be performed as part of the practice of medicine and which would be done whether or not study entry was contemplated, such as for diagnosis or treatment of a disease or medical condition, may be performed and the results subsequently used for determining study eligibility without first obtaining consent if done within the screening timeframe, and if the site's IRB is in agreement.

^l The radiation treatment area surface measurements can occur at any time before first day of radiation treatment.

^m Breast volume measurements are required for all patients who had breast conserving surgery (lumpectomy or partial mastectomy). Breast tissue should be defined per the [RTOG contouring guidelines \(RTOG 2009\)](#), but sites may use their local SOP for calculating breast volume.

ⁿ A serum pregnancy test will be performed at Screening for WOCBP or at any point in time if a pregnancy is suspected. All other pregnancy assessments will be urine pregnancy tests, unless site/local authority mandates serum pregnancy testing.

^o Study drug is to be dispensed to the patients at the scheduled study visits. Additional study drug will be dispensed to patients based on patient need, and will be recorded as an unscheduled study drug dispensation. Study drug (bottle + lotion) is to be weighed before study drug dispensing.

^p When radiation treatment overlaps with study drug administration and radiation treatment is in the morning, RTA 408 Lotion or vehicle should be applied to the breast area immediately after radiation treatment concludes. If radiation treatment is in the afternoon, RTA 408 Lotion or vehicle should be applied at least 4 hours before radiation treatment. RTA 408 Lotion or vehicle should also be applied nightly.

^q Planned radiation treatment must be no more than 7.5 weeks.

^r Radiation dermatitis assessments must be performed PRIOR to initiation of that day's radiation treatment, and only by a trained evaluator. If radiation treatment is delayed or extended, dermatitis assessments should be performed weekly until the end of radiation treatment.

^s The Skindex-16 must be completed prior to initiation of that day's radiation treatment.

^t Screening lab assessments (described in Section 9.8 for [chemistry](#), [hematology](#), [urinalysis](#), and [serum pregnancy tests](#)) should be drawn ≤ 14 days prior to randomization in order to have current values for inclusion/exclusion assessment.

^u A single PK collection will be obtained on Visit 3, Visit 6, Visit 9, Visit 11 and Visit 12. If patients are to receive a morning radiation treatment on any of these visits, the PK sample should be drawn after RTA 408 Lotion or Vehicle Lotion application, which occurs after the completion of radiation treatment. If patients are to receive an afternoon radiation treatment on any of these visits, the PK sample should be drawn after the radiation treatment.

^v Optional photographs may be collected at Sponsor-qualified sites. On Day 1 of radiation treatment and the last day of radiation treatment, photographs must be collected prior to radiation treatment.

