9.8.25. Dermatitis Assessment

The CTCAE v4.03 radiation dermatitis grade will be assessed by a local, trained physician, nurse or appropriately trained site staff member. Components of the CTCAE will be recorded separately by a local, trained physician, nurse or appropriately trained site staff member.

Dermatitis assessment at each visit is performed before initiation of radiation therapy. Dermatitis assessments must be performed by trained evaluator(s) at each time point indicated in [Table 3](#). These components include the severity of erythema, the extent and severity of dry desquamation, the extent and severity of wet desquamation and the presence of edema. Refer to Section [13.2.2.1](#) for the CTCAE scoring.

New or worsening of radiation dermatitis signs/symptoms should not be captured as individual AEs, but rather are captured in the Dermatitis Assessment process and documentation. These signs / symptoms are being assessed as study endpoints. Thus, if investigators seek to enter “radiation dermatitis”, “erythema”, “desquamation” or other signs / symptoms of radiation dermatitis as adverse events, they should first discuss the signs/symptoms with the medical monitor. The investigator, in coordination with the medical monitor, will determine the process for capturing these signs/symptoms.

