### 5.1 Primary Efficacy

The primary efficacy outcome of this study is the radiation dermatitis grade measured with Common Terminology Criteria for Adverse Events (CTCAE, Version 4.03) following 3D conformal radiation therapy to the breast and concomitant administration of RTA 408 Lotion (0.5% and 3%) compared to administration of vehicle. Radiation dermatitis scoring is assessed by a local, trained physician, nurse or appropriately trained site staff member based on CTCAE v4.03 on a scale of 0 to 5 (National Cancer Institute, 2010). Following randomization, patients will be evaluated in person at weekly visits during the administration of the study treatment up to a maximum of 13 weeks.

Longitudinal mixed-models will be used to analyze the dermatitis scores over time, incorporating the repeated measures design of the study. Treatment group and week of visit will constitute the main fixed effects of the model; study subject will represent the random effect; site, smoking status, and breast cancer treatment will be evaluated for inclusion in the model as covariates. The distribution of residuals will be examined using a Shapiro-Wilks test. Interactions of time and treatment effect will also be examined in the mixed-model.

A sensitivity analysis will be performed using the same model, except cumulative radiation (expressed as a categorical variable in 2.5 Gy increments from 0 to 70 Gy) will be used as a fixed effect instead of visit week. Only those CTCAE grades collected from baseline to the last day of radiation treatment for each patient will be considered for this sensitivity analysis.

The mean CTCAE dermatitis scores will also be plotted in a scatter plot by cumulative radiation exposure overall and by patient subsets of interest.

RTA 408 treatment arms will be compared with vehicle utilizing a hierarchical testing strategy described in Section 3.6.

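### Protocol Table 3 schedules no dermatitis grade at Visit 10, so the two on-drug weeks after radiation are graded only once, about 14 days out, although the text describes weekly evaluation.

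*Protocol*

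**What the plan says.** Protocol 9.8.25 makes the schedule table binding for the primary measurement: "Dermatitis assessments must be performed by trained evaluator(s) at each time point indicated in" Table 3. That row is marked at Visits 3 to 9, 11 and 12, and not at Visit 10.

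Visit 10 is a planned visit. Footnote f of Table 3 puts it about 7 days after the end of radiation, and footnote g puts Visit 11 about 7 days after that. Study drug continues for two weeks after radiation (Protocol 7.1), so both visits fall within the dosing period.

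The text describes a weekly rhythm. Protocol 7.1: "patients will be assessed in person at weekly visits during administration of study treatment". SAP 5.1, in the paragraph that defines the primary outcome: "patients will be evaluated in person at weekly visits during the administration of the study treatment up to a maximum of 13 weeks". SAP 5.2.1 takes each patient's maximum grade over weekly visits.

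Footnote r requires the grade to be taken before that day's radiation. It also says that "dermatitis assessments should be performed weekly until the end of radiation treatment", on the condition that radiation is delayed or extended.

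**The concern.** The primary objective is a time-averaged dermatitis grade. Secondary objectives are the maximum grade, success (maximum below 2) and the duration of grade ≥ 2. All four are built from the scheduled grades. In the first week after radiation the cumulative dose is at its highest and the lotion is still being applied, and the patient is seen without being graded.

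A reaction that rises and settles between Visits 9 and 11 leaves no trace in these endpoints. If no other visit shows grade ≥ 2, the patient counts as a success and her maximum is too low. In the time average, the post-radiation fortnight rests on a single late reading.

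**Working it through.** The plan states no figure on this point. The check is a reading of the table, a timeline, and an illustration under stated assumptions.

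**1. Is the blank real?** Protocol Table 3 has 12 visit cells per row.

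| Row | Visits marked, as read | Visit 10 |
|---|---|---|
| "Dermatitis assessment ^r" | 3–9, 11, 12 | blank |
| "Adverse event collection" | 2–12 | marked |
| PK sample | 3, 5, 9, 11, 12 | blank |

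The adverse event row shows that the Visit 10 column exists and is used. Footnote u fixes the right-hand columns: "A single PK collection will be obtained on Visit 3, Visit 6, Visit 9, Visit 11 and Visit 12". The PK row ends mark, blank, mark, mark for Visits 9 to 12, and the dermatitis row ends the same way. Some middle columns are shifted as read (PK appears at Visit 5 where the footnote says 6), but the end of the row is fixed by text.

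**2. Timeline.** Visit 9 is the last day of the boost (footnote e), and its grade is taken before that day's fraction (footnote r). Visit 11 is at 7 + 7 = 14 days. The gap between grades is therefore 14 days nominally, or 10 to 18 if both visits used the full ±2-day window.

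**3. Does anything else capture the grade?**
- Signs of radiation dermatitis are not routinely recorded as adverse events (Protocol 9.8.25, 12.2.1.1; SAP 7.1).
- Unscheduled grades stand in only for missing scheduled ones (SAP 3.7.3), and Visit 10 has no scheduled grade.
- For the same reason, worst-observation imputation (SAP 3.6) is not triggered.
- Endpoint summaries use scheduled visits (SAP 3.1).

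**4. Share of on-drug grades, assuming 6 weeks of radiation.** Visits 3 to 9 give 7 grades and Visit 11 gives 1. The post-radiation fortnight supplies 1/8 = 12.5%. With Visit 10 it supplies 2/9 = 22%.

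**5. Chance of missing an episode.** Assume onset uniform over a gap of G days and an episode of L days. It is missed with probability max(0, (G − L)/G). As scheduled, G = 14; with a Visit 10 grade there are two gaps of 7.

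| Episode length | As scheduled | With Visit 10 |
|---|---|---|
| 3 days | 79% | 57% |
| 5 days | 64% | 29% |
| 7 days | 50% | 0% |
| 10 days | 29% | 0% |
| 14 days | 0% | 0% |

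At the window limits, the scheduled figure for 7 days runs from 3/10 = 30% to 11/18 = 61%. The 0% is also nominal: if Visit 10 fell two days late, the gaps would be 9 and 5 days and the figure would be (9 − 7)/14 = 14%.

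**6. Direction between arms.** Assume true success of 30% on vehicle and 50% on active, and let a share q of failures be visible only inside the gap. Observed success is p + (1 − p)q.
- q = 10% in both arms: 37% against 55%, a difference of 18 points instead of 20.
- q = 20% vehicle, 5% active: 44% against 52.5%, a difference of 8.5.
- q = 5% vehicle, 20% active: 33.5% against 60%, a difference of 26.5.

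The difference can shrink or grow, depending on quantities that the documents do not give.

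**The case against.** The strongest reply is that the point rests on one blank cell in a table that is imperfectly read, and that the narrative already calls for weekly evaluation, so only a consistency check is needed. Part of this stands. SAP Appendix 1 cannot be used as confirmation. Its grid as read has 13 cells for 12 visits, and its adverse event row is blank in the same cell as its dermatitis row. On one alignment its 10 dermatitis marks would be Visits 3 to 12, which includes Visit 10. A reader might infer that both documents omit the grade; the SAP does not settle it. The Protocol cell is better supported, by footnote u and by the adverse event row, and Protocol 9.8.25 sends sites to the table rather than to the narrative.

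A reader might also infer that footnote r ends routine grading when radiation ends. It does not, because its sentence covers only delayed or extended radiation.

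A reader might infer that the gap pulls the arms together because the worse arm loses more episodes. That is not shown. Shorter episodes are missed more often, so a lotion that shortened them could hide more active-arm episodes. Severe vehicle reactions may already be visible at Visit 9 or still present at Visit 11.

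Visit 9 lacks only one fraction: with an assumed 1.8 to 2 Gy against totals of 55 to 66.4 Gy, that is 1.8/66.4 = 2.7% to 2/55 = 3.6% of the dose. The issue is therefore the 14-day interval, not a large dose shortfall at Visit 9.

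Finally, 1 of 8 grades could be set against 14 of 56 days (25%) to claim a twofold under-weighting. The plan specifies a mixed model with visit week as a fixed effect, not a day-weighted mean, so that comparison is not used here.

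**Conclusion.** The point holds as a schedule gap and an inconsistency that should be corrected. As Table 3 stands, the only on-drug grade after radiation is complete comes about 14 days later, and a planned on-drug visit passes without the primary measurement. What can be lost is a peak, or a grade ≥ 2 episode, lying wholly between Visits 9 and 11. Anything present at either visit is still recorded, and on the nominal schedule an episode of 14 days or more cannot be missed.

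The firm figures are the 14-day gap and, given 6 weeks of radiation, 1 of 8 on-drug grades instead of 2 of 9. The 50% for a 7-day episode rests on uniform onset and an assumed length, and applies only to episodes that start in the gap. It does not mean that half of all reactions are lost. The documents do not say when dermatitis peaks or how long it lasts, so neither the loss to the endpoints nor the direction of bias can be stated.

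**What to change.** - Mark the dermatitis assessment at Visit 10 in Protocol Table 3.
- Check the same cell in SAP Appendix 1 and make it agree.
- Include the Visit 10 grade in the visit factor of the primary mixed model and in the maximum, success and duration endpoints.
- Leave footnote r's sentence on delayed or extended radiation in place; a short clarification that routine grading follows the table would be enough.

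The table then matches the weekly evaluation described in Protocol 7.1, SAP 5.1 and SAP 5.2.1. The cost is a schedule amendment, plus one short grading and one eCRF page per patient (about 177 in all). The visit already exists, and the evaluators are those who grade at the other visits.
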